discontinued following single events each of cerebral hemorrhage and intracranial hemorrhage. Interrupt ponatinib for serious or severe hemorrhage and evaluate

Fluid Retention

Ponatinib is associated with edema and occasionally serious fluid retention. Patients should be weighed and monitored regularly for signs and symptoms of fluid retention. An unexpected rapid weight gain should be carefully investigated and appropriate treatment provided. Interrupt, reduce the dose of, or discontinue ponatinib according to the recommendations for non-hematologic toxicity.

One or more fluid retention AEs occurred in 125 (27.8%) patients in this study. The most common events were peripheral edema (16.7%), pleural effusion (7.6%), and pericardial effusion (3.8%). In AP24534-10-201, serious fluid retention events were observed in 4% (18/449) of patients treated with ponatinib. One instance of brain edema in a blast phase-CML patient with post-craniotomy was fatal. Serious fluid retention events in more than 1 patient included: pleural effusion (6/449), pericardial effusion (6/449, 1%), and ascites (2/449, <1%). In most cases, patients were able to continue ponatinib therapy without dose reductions or interruptions. Ponatinib was discontinued for three patients, due to pericardial effusion in two, and pleural effusion in one.

Cardiac Arrhythmias

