6. DOSING DELAYS/DOSE MODIFICATIONS

6.1 Dose Modifications for Ponatinib

A maximum of two ponatinib dose level reductions are allowed. If a third dose level reduction is required, treatment will be permanently discontinued. The starting dose for ponatinib is 45 mg oral daily.

Patients who experience a vascular (arterial or venous) occlusive event should be immediately discontinued from the study and ponatinib should not be restarted. For serious reactions other than arterial or venous occlusion, do not restart until the serious event has resolved.

Dose Modifications

Dose Level	Ponatinib Dose/Schedule
0	45 mg daily
-1	30 mg daily
-2	15 mg daily

Dose Modification for Nausea

Nausea and vomiting are reported with ponatinib. The use of an antiemetic prophylactically is not recommended. However, if a patient is symptomatic, appropriate antiemetic medications may be used as clinically indicated.

CTCAE Grade	Action and Dose Modification
≤ Grade 1	No change in dose
Grade 2	Occurrence at 45 mg: 
• Interrupt ponatinib and resume at 45 mg after recovery to ≤ Grade 1 Occurrence at 30 mg: 
• Interrupt ponatinib and resume at 30 mg after recovery to ≤ Grade 1 Occurrence at 15 mg: 
• Discontinue ponatinib
Grade 3	Occurrence at 45 mg: 
• Interrupt ponatinib and resume at 30 mg after recovery to ≤ Grade 1 Occurrence at 30 mg: 
• Interrupt ponatinib and resume at 15 mg after recovery to ≤ Grade 1 Occurrence at 15 mg: 
• Discontinue ponatinib
Grade 4	Off protocol therapy

**Patients requiring > two dose reductions should go off protocol therapy.*

Recommended management: Anti-emetics.

Dose Modification for Vomiting

CTCAE Grade	Action and Dose Modification
≤ Grade 1	No change in dose
Grade 2	Occurrence at 45 mg: • Interrupt ponatinib and resume at 45 mg after recovery to ≤ Grade 1 Occurrence at 30 mg: • Interrupt ponatinib and resume at 30 mg after recovery to ≤ Grade 1 Occurrence at 15 mg: Discontinue ponatinib
Grade 3	Occurrence at 45 mg: • Interrupt ponatinib and resume at 30 mg after recovery to ≤ Grade 1 Occurrence at 30 mg: • Interrupt ponatinib and resume at 15 mg after recovery to ≤ Grade 1 Occurrence at 15 mg: Discontinue ponatinib
Grade 4	Off protocol therapy

*Patients requiring > two dose reductions should go off protocol therapy.

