While myelosuppression can occur any time during treatment, its onset most commonly occurs within the first month on treatment. Ponatinib has not been studied in solid tumor patients and whether (or to what extent) myelosuppression will occur in these patients is unknown.

	Action and Dose Modification
Absolute Neutrophil Count (ANC) < 1 x 10 ⁹ /L Or Platelets < 50 x 10 ⁹ /L	
First Occurrence
 
 • Interrupt ponatinib and resume initial dose after recovery to ANC ≥ 1.5 x 10⁹/L and platelet ≥ 75 x 10⁹/L 
Second Occurrence
 
 • Interrupt ponatinib and resume at 30 mg after recovery

	Action and Dose Modification
	
to ANC $\geq 1.5 \times 10^9/L$ and platelet $\geq 75 \times 10^9/L$
 
Third Occurrence
 
 • Interrupt ponatinib and resume at 15 mg after recovery to ANC $\geq 1.5 \times 10^9/L$ and platelet $\geq 75 \times 10^9/L$

Dose Modifications for Hemorrhage

Concomitant use of ponatinib with anticoagulants should be approached with caution in patients who may be at risk of bleeding events. Serious bleeding events, including fatalities have been reported in patients treated with ponatinib. Most hemorrhagic events, but not all, occurred in patients with grade 4 thrombocytopenia. Interrupt ponatinib for serious or severe hemorrhage and evaluate.

CTCAE Grade	Action and Dose Modification
Grade 1	No intervention
Grade 2	
Occurrence at 45 mg:
 
 • Interrupt ponatinib and resume at 30 mg after recovery to \leq Grade 1 
Occurrence at 30 mg:
 
 • Interrupt ponatinib and resume at 15 mg after recovery to \leq Grade 1 
Occurrence at 15 mg:
 
 • Discontinue ponatinib
Grade 3 or 4	Permanently discontinue ponatinib

Dose Modifications for Pancreatitis / Lipase Elevations

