Pancreatitis (symptomatic abdominal pain associated with pancreatic enzyme elevation) and/or elevations in lipase and amylase are known AEs associated with ponatinib. Most cases of pancreatitis or elevated pancreatic enzymes occur within the first 2 months of treatment with ponatinib. Patients with low-grade (1 or 2) elevation in enzymes can be continued without dose reduction but should be monitored closely with serial enzyme level determinations. Patients can continue with ponatinib treatment at the same or a reduced dose once the event has improved to grade 1 or resolved. See below for dose-modification guidelines.

CTCAE Grade	Action and Dose Modification
Asymptomatic Grade 1 or 2 elevation of serum lipase	Consider interruption or dose reduction of ponatinib
Asymptomatic Grade 3 or 4 elevation of lipase ($> 2 \times$ ULN*) or asymptomatic radiologic pancreatitis (Grade 2 pancreatitis)	
Occurrence at 45 mg:
 
 Interrupt ponatinib and resume at 30 mg after recovery to \leq Grade 1 ($< 1.5 \times$ ULN) 
Occurrence at 30 mg:
 
 Interrupt ponatinib and resume at 15 mg after recovery to \leq Grade 1 
Occurrence at 15 mg:
 
 Discontinue ponatinib
Symptomatic Grade 3 pancreatitis	
Occurrence at 45 mg:
 
 Interrupt ponatinib and resume at 30 mg after complete resolution of symptoms and after recovery of lipase elevation to \leq Grade 1 
Occurrence at 30 mg:
 
 Interrupt ponatinib and resume at 15 mg after complete resolution of symptoms and after recovery of lipase elevation to \leq Grade 1 
Occurrence at 15 mg:
 
 Discontinue ponatinib
Grade 4 pancreatitis ($> 5 \times$ ULN of lipase)	Discontinue ponatinib

*ULN = Upper Limit of Normal for the lab

Dose Modifications for Skin Rash

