Skin rashes have been commonly reported in patients taking ponatinib. The vast majority of the skin events are nonserious, either self-limiting or manageable with antihistamines or topical steroids, and do not result in discontinuation. In more severe cases, a short course of oral corticosteroids may be used until the rash has improved or resolved. In patients treated with ponatinib, the most common skin manifestations are a diffuse maculopapular rash that is non-pruritic or an acneiform dermatitis. Occasionally, patients treated with ponatinib have been reported to have a dry, flaky or exfoliative type of rash or psoriasiform dermatitis. Rarely, an erythema multiforme type of rash has been associated with ponatinib.

CTCAE Grade	Action and Dose Modification
Grade 2 persistent* despite optimal symptomatic therapy, but not clinically significant	No change, continue ponatinib therapy, continue monitor every 2 weeks.

CTCAE Grade	Action and Dose Modification
Grade 2 persistent* despite optimal symptomatic therapy, is clinically significant	
Hold ponatinib
 
Resume at 45 mg after recovery to \leq grade 1
 
Recurrence at 45 mg: Hold ponatinib
 
Resume at 30 mg after recovery to \leq grade 1
 
Recurrence at 30 mg: Hold ponatinib
 
Resume at 15 mg after recovery to \leq grade 1
 
Recurrence at 15 mg: Discontinue ponatinib

Grade 3 persistent* despite optimal symptomatic therapy, but not clinically significant	
No change, continue ponatinib therapy, continue monitor every 2 weeks.

Grade 3 persistent* despite optimal symptomatic therapy, is clinically significant	
Hold ponatinib
 
Resume at 30 mg after recovery to \leq grade 1
 
Recurrence at 30 mg: Hold ponatinib
 
Resume at 15 mg after recovery to \leq grade 1
 
Recurrence at 15 mg: Discontinue ponatinib

*Persistent rash is defined as 7 days.

Guidelines for Supportive Care of Rash	
Type of Care	Action
Prevention/Prophylaxis	
 Avoid unnecessary exposure to sunlight. Apply broad-spectrum sunscreen (containing titanium dioxide or zinc oxide) with a skin protection factor (SPF) ≥ 15 at least twice daily. Use thick, alcohol-free emollient cream (e.g., glycerine and cetomacrogol cream) on dry areas of the body at least twice daily.

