Dose Modifications for Ocular Toxicity

Ocular toxicities have occurred in clinical trials of ponatinib. Serious ocular toxicities leading to blindness or blurred vision have occurred in ponatinib-treated patients. Patients are required to have a standard ophthalmic exam performed by an ophthalmologist at baseline and as clinically warranted. The exam will include indirect fundoscopic examination, visual acuity (corrected), visual field examination, tonometry, and direct fundoscopy.

Retinal toxicities including macular edema, retinal vein occlusion, and retinal hemorrhage have occurred in ponatinib-treated patients.

Grade	Management Guideline	Dose Modification
Grade 1 Asymptomatic or symptomatic but not limiting ADL; intervention not indicated.	
 Consult ophthalmologist within 7 days of onset. Exclude ME, RVO, or RH. Consult retinal specialist if available in case of ME, RVO, or RH Continue follow up examination(s) (by retinal specialist if available) for ME, RVO, or RH 	
 Continue ponatinib at the same dose level until ophthalmologic examination can be conducted.* If ophthalmologic examination cannot be performed within 7 days of onset, interrupt ponatinib until ME, RVO, or RH can be excluded and symptoms resolve. If ME, RVO, or RH excluded restart ponatinib at same dose level. If ME: Permanently discontinue ponatinib. If RVO: Permanently discontinue ponatinib. If RH: Permanently discontinue ponatinib.
Grade 2 and 3 Grade 2 defined as: Symptomatic with moderate decrease in visual acuity (20/40 or better; limiting instrumental ADL; local or non-invasive intervention indicated. Grade 3 defined as: Symptomatic with marked decrease in visual acuity or marked visual field defect (worse than 20/40 but better than 20/200); severe pain or medically significant; operative intervention indicated.	
 Consult ophthalmologist immediately. Exclude ME, RVO, or RH. Consult retinal specialist in case of ME, RVO, or RH for follow-up exam. Continue follow up examination(s) (by retinal specialist if available) for ME, RVO, or RH. 	
 Interrupt ponatinib until signs and symptoms have resolved to baseline. If ME, RVO, or RH excluded and symptoms resolved to baseline, restart ponatinib reduced by one dose level. If ME: Permanently discontinue ponatinib. If RVO: Permanently discontinue ponatinib. If RH: Permanently discontinue ponatinib.

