Asymptomatic	Absolute decrease of >10% in LVEF compared to baseline and ejection fraction below the institution's LLN.	
 • Interrupt ponatinib and repeat ECHO within 4 weeks. • If the LVEF recovers within 4 weeks (defined as LVEF \geqLLN and absolute decrease \leq10% compared to baseline): 
 – Restart treatment with ponatinib at reduced dose by one dose level. – Repeat ECHO 4 and 12 weeks after re-start; continue in intervals of 12 weeks thereafter. • If LVEF does not recover within 4 weeks: 
 – Consult with cardiologist. – Permanently discontinue Ponatinib. – Repeat ECHO after 4, 8, 12 weeks or until resolution.
Symptomatic^b	
 • Grade 3: resting LVEF 39-20% or >20% absolute reduction from baseline • Grade 4: Resting LVEF \leq20%. 	
 • Permanently discontinue ponatinib. • Report as SAE. • Consult with cardiologist. • Repeat ECHO after 4, 8, and 12 weeks or until resolution.

^a Symptoms may include: dyspnea, orthopnea, and other signs and symptoms of pulmonary congestion and edema.

Treatment delays at the start of treatment that are unrelated to drug will require restaging of the patient and re-initiating treatment. If at any time during the course of the trial, treatment is delayed over 3 weeks due to events unrelated to drug, treatment will resume as normal once the patient is deemed stable to continue.

Dose Modifications for General Non-hematologic Toxicities

CTCAE Grade	Action and Dose Modification
-------------	------------------------------

Grade 1 or transient Grade 2	No intervention
Grade 2 lasting \geq 7 days with optimal care	Hold ponatinib Resume at 45 mg after recovery to \leq grade 1 Recurrence at 45 mg: Hold ponatinib Resume at 30 mg after recovery to \leq grade 1 Recurrence at 30 mg: Hold ponatinib Resume at 15 mg after recovery to \leq grade 1 Recurrence at 15 mg: Discontinue ponatinib
Grade 3 or 4	Hold ponatinib Resume at 30 mg after recovery to \leq grade 1 Recurrence at 30 mg: Hold ponatinib Resume at 15 mg after recovery to \leq grade 1 Recurrence at 15 mg: Discontinue ponatinib

Dose Modification for concurrent strong CYP3A inhibitors

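### Four Section 6.1 tables give resume doses that ignore the current dose, so a patient already reduced can be told to restart higher after a new toxicity

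*Combined protocol and SAP*

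**What the plan says.** Section 6.1 sets three dose levels (45, 30 and 15 mg daily), allows at most two reductions, and states: "If a third dose level reduction is required, treatment will be permanently discontinued". It then writes its toxicity tables in different styles.

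- **Tied to the current dose.** Nausea, vomiting, diarrhea, hepatic toxicity, hemorrhage and lipase/pancreatitis have separate lines for an *occurrence* at 45, 30 and 15 mg. The pancreatitis text says: "Patients can continue with ponatinib treatment at the same or a reduced dose once the event has improved to grade 1 or resolved".
- **Relative to the current level.** After a resolved ocular Grade 2 or 3 event the instruction is to "restart ponatinib reduced by one dose level". After LVEF recovery it is "Restart treatment with ponatinib at reduced dose by one dose level". The hypertension table also restarts at a reduced dose once an interruption has been needed.
- **Fixed for the first event.** In the clinically significant rash rows and the neuropathy and general non-hematologic tables, the first-event line for Grade 2 is "Resume at 45 mg after recovery to" Grade 1 or lower. For Grade 3 (rash) or Grade 3 or 4 (the other two) it is "Resume at 30 mg after recovery to" Grade 1 or lower. Only the later lines depend on dose, and they are labelled *recurrence*.
- **By occurrence number.** For myelosuppression the first occurrence reads "Interrupt ponatinib and resume initial dose after recovery to ANC" and platelet thresholds are met. The second gives 30 mg and the third 15 mg.

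**The concern.** The fixed lines work for a patient still on the 45 mg starting dose. They do not work for a patient already reduced for a different toxicity. That patient's new event is a first event of its kind, so it falls on the fixed line and not on a recurrence line.

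Such patients should be expected. Section 5.1 reports that 59% of patients in the CML and ALL trials needed reduction to 30 or 15 mg. Section 2.2.1 reports that 26% of patients in the GIST study needed a reduction or an interruption of at least three days, without separating the two. Section 6.1 also puts patients on a strong CYP3A inhibitor at 30 mg.

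Safety is at stake. Section 2.2.1 describes exposure as roughly proportional to dose from 15 to 60 mg, and reports more grade 3 or higher reactions, including rash, neutropenia and thrombocytopenia, with higher dose intensity. The general table is also the catch-all. Section 2.2.1 sends fluid retention, and QTcF prolongation attributed to ponatinib, to the non-hematologic rules, and neither has its own table in Section 6.1. No effect on the primary endpoint or on the planned tolerability count is claimed.

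**Working it through.** The plan gives no figure to reproduce. The check compares each printed resume dose with each possible current dose.

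**Inputs (all Section 6.1).** Rash, neuropathy and general non-hematologic: 3 tables × 2 first-event lines = 6 targets (Grade 2 → 45 mg; Grade 3 or 3/4 → 30 mg). Myelosuppression: 3 targets (first → initial dose, second → 30 mg, third → 15 mg). That is 6 + 3 = 9 targets at each of three current doses, or 27 cells, of which 9 × 2 = 18 are at a reduced dose.

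**Rule.** A cell is *raise*, *same* or *lower* according to whether the resume dose is above, equal to or below the current dose. Here initial dose is read as 45 mg.

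| Resume line | At 45 mg | At 30 mg | At 15 mg |
|---|---|---|---|
| Grade 2 first event → 45 mg (3 tables) | 3 same | 3 raise | 3 raise |
| Grade 3 or 3/4 first event → 30 mg (3 tables) | 3 lower | 3 same | 3 raise |
| Myelosuppression, first → 45 mg | same | raise | raise |
| Myelosuppression, second → 30 mg | lower | same | raise |
| Myelosuppression, third → 15 mg | lower | lower | same |
| **Raise / same / lower** | **0 / 4 / 5** | **4 / 4 / 1** | **8 / 1 / 0** |

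Reduced doses: 4 + 8 = 12 raise, 4 + 1 = 5 same, 1 + 0 = 1 lower, of 18. All doses: 12 raise, 9 same, 6 lower, of 27.

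**Alternative reading.** If initial dose means the dose before the interruption, the first myelosuppression line becomes *same* everywhere. The counts are then 3 / 5 / 1 at 30 mg and 7 / 2 / 0 at 15 mg: 10 raise, 7 same, 1 lower, of 18.

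**Denominator.** The third myelosuppression line can never raise the dose. Leaving it out gives 8 × 2 = 16 reduced-dose cells, with 12 (or 10) raising the dose.

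**Size of each step.** 30 → 45 mg is 45/30 = 1.5 times the dose, 15 → 30 mg is 30/15 = 2 times, and 15 → 45 mg is 45/15 = 3 times.

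**The sharpest case.** A patient at 15 mg has already used both reductions and then has a first Grade 3 event under the general table. The first-event line says 30 mg. The same cell discontinues a recurrence at 15 mg, and the opening rule of Section 6.1 discontinues any patient who needs a third reduction. So the patient's dose is either doubled or stopped for good, depending on which line is followed.

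**The case against.** The strongest case on the other side is that each disputed cell is meant as a descending ladder from the starting dose: 45, 30, 15, stop. Section 6.1 shows only downward levels and gives no re-escalation procedure, and a sensible investigator would not raise a dose straight after a toxicity. The ladder reading is plausible and probably what was meant. It is not what is written. *Recurrence* means the same toxicity returning, so a new toxicity in a patient reduced for another reason falls on the unconditional first line. The limit on reductions does not block an increase.

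It can also be said that the referring text contradicts any increase. For fluid retention Section 2.2.1 says "Interrupt, reduce the dose of, or discontinue ponatinib according to the recommendations for non-hematologic toxicity", and the QTcF text likewise speaks of interruption and reduction. That is true and shows that no increase was intended, but it leaves the referring text in conflict with the table it points to. Section 2.2.1 also allows resumption at an unchanged dose after constitutional symptoms. That is background on one symptom group and sets no general limit.

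Three limits stand. The list of reactions that rose with dose intensity does not include fluid retention, QTcF prolongation or neuropathy, so that evidence bears on rash and myelosuppression. Cell counts weigh every cell equally, however rarely it is reached. Finally, the nausea, vomiting, diarrhea and hemorrhage tables stop treatment for Grade 2 at 15 mg, so allowing a first Grade 2 event to resume at 15 mg in the re-keyed tables is a choice, not strict alignment. It keeps the present principle in the three tables that a first Grade 2 event costs no reduction.

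**Conclusion.** The concern holds. Section 6.1 as written can tell a patient on a reduced dose to resume at a higher one after a new toxicity. This happens in 12 of 18 reduced-dose cells, or 10 of 18 on the narrower reading of initial dose. At the 45 mg starting dose no line raises the dose. The problem is greatest at 15 mg, where 8 (or 7) of 9 lines do.

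The conclusion assumes that *recurrence* refers to the same toxicity and that the first-event lines are followed literally. The counts describe table cells and not risk; how many patients would be affected cannot be worked out from the documents. The point should be corrected because the dosing rule is wrong as written, not merely short of detail.

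**What to change.** Re-key the four tables to the dose at the time of the event.

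- **Rash (clinically significant), neuropathy, general non-hematologic.** Use *occurrence* lines at 45, 30 and 15 mg. A first Grade 2 event resumes at the current dose, and the existing Grade 2 recurrence lines stay. A Grade 3 or 4 event (Grade 3 for rash) resumes one level below the current dose, with discontinuation at 15 mg.
- **Myelosuppression.** The first occurrence resumes at the dose in use when it began. Later occurrences step down one level from the current dose, with discontinuation if a third reduction would be needed.

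For a patient starting at 45 mg with no other reduction, this reproduces the present instructions. With these rules none of the reduced-dose cells raises the dose.

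A sentence barring resumption above the dose at which the event occurred is a useful safeguard. It cannot replace the re-keying, because alone it would let a Grade 3 or 4 event at 15 mg resume at 15 mg.

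The cost is protocol wording in four tables, with no extra patients or procedures.

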7. ADVERSE EVENTS AND SERIOUS ADVERSE EVENTS: LIST AND REPORTING REQUIREMENTS

Expected adverse events include the adverse reactions that have at least possible relationship to ponatinib and are considered expected in ponatinib clinical studies. To mitigate the inherent risks in clinical studies of ponatinib, patients should be monitored closely while receiving treatment. A list of AEs (**Section 7.2**) for ponatinib is listed.

7.1 Definitions

7.1.1 Adverse Event

An AE is any untoward medical occurrence in a patient or clinical investigation subject administered a pharmaceutical product and which does not necessarily have to have a causal

relationship with the treatment. An AE can be any unfavorable and unintended sign (including an abnormal laboratory finding), symptom, or disease temporally associated with the use of a medicinal product whether or not considered related to the medicinal product. Any worsening of a preexisting condition, which is temporally associated with the use of the study drug (ie, occurs after the first dose of study drug), is also an AE.

AEs include:

- Abnormal test findings
- Changes in physical examination findings
- Other untoward medical events, regardless of their relationship to the study drug, such as injury, events that require surgery, accidents, or apparently unrelated illnesses
- Hypersensitivity

Additionally, AEs may include signs or symptoms resulting from:

- Drug overdose
- Drug withdrawal
- Drug abuse
- Drug misuse
- Drug interactions
- Drug dependency
- Exposure in utero

